4.5 STUDY RELATED INFORMATION

HAMS-AB will be in the form of acetylated and butyrylated HYLON® VII corn starch [a resistant corn starch type 2 (RS2) derived from high amylose maize starch and containing approximately 70% amylose that has been acetylated and butyrylated. It will be provided by Ingredion Incorporated, Bridgewater, NJ. A computer-based randomization plan will be prepared by the PI. Randomization lists will be kept by the PI.

HAMS is a resistant corn starch type 2 dietary supplement which is high in certain foods such as potatoes and green unripe bananas. RS2 is not digested in the small intestine and acts as a dietary fiber. Many short chain fatty acids (SCFAs), including acetic, propionic, and butyric acid, are formed normally during bacterial fermentation in the gut after fiber intake. Therefore, there are no expected adverse effects in general. Similarly, we do not expect any adverse effects during pregnancy. However, to be safe, female subjects who are pregnant or anticipating pregnancy will not be enrolled and pregnancy tests will be done for females of reproductive potential at all visits.

HAMS has a satisfactory safety profile based on exposure in adults and pediatrics given that it is a dietary supplement available over the counter. To date, there has been no indication of specific organ class toxicity. Additionally, there has been no indication of a particular pattern of event clustering or increased individual safety risk, and no increased vulnerabilities or major risks have been identified for the T1D and pediatric population.

50 –ELIGIBILITY

51 INCLUSION CRITERIA

Patients must meet all the following criteria:

- Be between 11-17 years of age
- Willing to consume HAMS-AB and follow a diabetic diet
- Diagnosed by ADA criteria [45] with T1D in the last 4-36 months
- Random non-fasting C-peptide of 0.17nmol/L or greater
- Willing to use an effective form of contraception if sexually active

- BMI < 85% for age and sex
- Positive for any one of the following diabetes-related autoantibodies that are tested clinically [IAA (if tested within 14 days of diagnosis), GAD, IA-2, or ZnT8].

52 EXCLUSION CRITERIA

Individuals who meet any of the exclusion criteria during the study will be replaced. However, participants may re-enroll if in the future, meet all eligibility requirements. Participants who re-enroll will need to be reassessed for their starting point. Participants must NOT meet any of the following criteria during enrollment re-entry or re-enrollment:

1. Presence of severe, active disease that interferes with dietary intake or requires the use of chronic medication, with the exception of well-controlled hypothyroidism and mild asthma not requiring oral steroids.
2. Diabetes other than T1D (Known monogenic forms of diabetes, Type 2 diabetes)
3. Chronic illness known to affect glucose metabolism (e.g., Cushing syndrome, polycystic ovarian disorder, cystic fibrosis) or taking medications that affect glucose metabolism (e.g., steroids, metformin)
4. Psychiatric impairment or current use of anti-psychotic medication
5. Any condition that, in the investigator's opinion, may compromise study participation or may confound the interpretation of the study results.
6. Female participants of child-bearing age with reproductive potential, must not be pregnant and agree to use an effective form of birth control or be abstinent during the study period (see below)
7. History of recurrent infections
8. History of on-going infections or antibiotic treatment within the past 4-6 weeks
9. History of immune compromise
10. Steroid intake (inhaled or oral)
11. Other immunosuppressant use in past 6 months
12. History of gastrointestinal disease
13. Possible or confirmed celiac disease
14. Pregnancy or possible pregnancy
15. Allergy to corn (prebiotic)
16. Allergy to milk or milk products or soy present in Boost
17. Participation in other intervention research trials within the past 3 months
18. Anticipate major changes in diabetes management during study (change from injection to pump, start of CGM usage if not already using one)
19. Consuming high fiber or vegetarian diet (consuming three or more servings of high fiber foods on 4 or more days per week) by history.
20. If taking fiber supplements or probiotics, unwilling to stop for the duration of the study.

Although generally considered to be safe, this has not been specifically studied in pregnant women and therefore, females of childbearing age will be asked to use effective Forms of Birth Control – any one of the following (additionally, participants will be counseled on the use of a second method of contraception):

- a. Use of oral, injected, or implanted hormonal methods of contraception or other forms of hormonal contraception that have comparable efficacy (failure rate <1%), for example, hormone vaginal ring or transdermal hormone contraception
- b. Placement of an intrauterine device (IUD) or intrauterine system (IUS)
- c. Barrier methods of contraception: Condom or Occlusive cap (diaphragm or cervical/vault caps) with spermicidal foam/gel/film/cream/vaginal suppository

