3.1 STUDY DESCRIPTION

This study will be a single center, controlled, randomized trial in young individuals newly diagnosed with type 1 diabetes. We are enrolling youth with new onset T1D with documented continued residual C-peptide production. Within 30 days of screening during which eligibility will be determined, subjects will have a 4-week treatment period with HAMS-AB or will be provided with guidelines on the generally recommended diabetic diet for youths with T1D [49, 50]. After a 4-week wash-out period the durability of effect will be assessed in those who received the prebiotic and during this washout period, both the study and control arm will be permitted to consume a regular diet. This design has been used in other studies of prebiotic administration with a 3–4-week intervention period and a 3–4-week washout phase [21, 32, 33]. Subjects will then cross over to either HAMS-AB or diet control for another 4 weeks.

A full dosing description can be found in section 6.2.

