32 STUDY DURATION

This study will screen up to 24 subjects at a single center (see Enrollment below). 12 subjects will be enrolled after meeting all eligibility criteria. If at any time during the study, a participant does not meet eligibility, participation in the study will be on hold until subject meets all eligibility criteria again. Participants may re-enter or re-enroll in the study if in the future, meet all eligibility requirements. Participants who re-enter or re-enroll will need to be reassessed for their starting point. Subjects who miss 20% of prebiotic doses (11 of 56 doses) will be replaced. The study will include the following periods:

- (1) Screening visit and eligibility determination (up to 30 days).
- (2) 4-week intervention period or diet guideline
- (3) 4-week washout period
- (4) 4-week intervention period or diet guideline.

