6.4 STUDY VISITS

Visit 1 – Screening

This visit will be at the hospital or research center. It will last approximately 1-2 hours and will include:

- Obtain informed consent/assent documents and determine inclusion and exclusion criteria
- Measurement of height and weight to determine BMI percentile eligibility and physical exam including pubertal staging
- Obtaining Vital signs (heart rate, temperature, blood pressure, and respiratory rate)
- Obtaining medical history
- Dietary assessment by verbal recall
- Obtaining blood sample (approximately 1.5 tablespoon) – Random non-fasting c-peptide, pancreatic autoantibodies if not previously done to confirm T1D diagnosis
- For female adolescents: urine will be collected for a pregnancytest
- Subject to sample prebiotic for palatability to ensure compliance

Visit 2 – Baseline-Intervention

This visit will be at the hospital or research center. It will last approximately 1-2 hours and will include:

- Measurement of weight and bedside nurse assessment such as general appearance, respiratory and cardiac assessment.
- Obtain vital signs (heart rate, temperature, blood pressure, and respiratory rate)
- Collecting a diet history (diary or questionnaire)
- Collecting Adverse Events (if applicable)
- Obtaining medical history and insulin use

Obtaining blood samples (approximately 2 tablespoons) – HbA1c, Serum biomarkers of beta cell stress and death (PI:C and INS DNA), other T1D testing, and serum and plasma for storage.

- Some of the blood will be stored for future T1D research use

- CGM placement and training for participants not currently using one.
- For female adolescents: urine will be collected for a pregnancytest
- Collecting stool samples prior to or the morning of the visit (a stool collection kit will be shipped to the participants once eligibility is confirmed)
- Study Randomization to either supplement or standard of care diabetes management and a diabetic diet.
– Supplement (HAMS-AB) will be provided and will be taken by mouth twice daily with food such as apple sauce or oatmeal as described in Section 6.2. Instructions will be provided for recommendations on a healthy diabetic diet.
- A new stool collection kit will be provided for the next visit

Visit 3 - Washout

This visit will be at the hospital or research center. It will last approximately 2-4 hours and will include:

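### Criterion 20 sets no minimum supplement-free interval before the Visit 2 stool, so the period-1 microbiome baseline of a prior fiber or probiotic user can still reflect the old product

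*Combined protocol and SAP*

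**What the plan says.** Section 5.2, criterion 20, deals with prior use in one line: "If taking fiber supplements or probiotics, unwilling to stop for the duration of the study". It gives no stop date and no minimum time off product.

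Section 3.1 places the start of treatment as follows: "Within 30 days of screening during which eligibility will be determined". The schedule in section 6.3 likewise sets Visit 2 at no more than 30 days after Visit 1. Both are upper limits; neither sets a lower one. For Visit 2, section 6.4 notes that "a stool collection kit will be shipped to the participants once eligibility is confirmed". Section 6.3 has each stool collected at home within 3 days of its visit. Randomization and the first supply of HAMS-AB also fall at Visit 2.

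Elsewhere the plan does set intervals for exposures that may affect the gut. Section 3.2 provides a "4-week washout period" between the periods, and section 6.3 puts Visit 4 at 28 days after Visit 3, give or take 3 days. Criterion 8 excludes participants with "antibiotic treatment within the past 4-6 weeks".

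Section 8.0 names change in the gut microbiome profile as the primary outcome and calculates a diversity index before and after the intervention for each recipient.

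**The concern.** For anyone randomized to HAMS-AB first, the Visit 2 stool is the pre-intervention sample. A participant who took a fiber supplement or probiotic until shortly before Visit 2 brings some of that product's effect into the sample. Its loss during period 1 is then counted as part of the period-1 change. If the old product acted in the same direction as HAMS-AB, its withdrawal offsets the HAMS-AB change in a HAMS-AB-first participant. In a control-first participant it appears as a fall under control. SCFA results would be affected in the same way.

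The two period baselines are also not protected equally. Visit 4 always follows a planned supplement-free interval, while Visit 2 may not. Section 8.0 says that the trial exists to estimate effect sizes for later trials, so an avoidable distortion of the baseline bears on its main product.

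**Working it through.** The plan states no figure on this point to reproduce. The sample size of 12 is a cited pilot rule of thumb, with no effect size, SD or power attached.

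**1. Time off product before each baseline stool**

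- Visit 4 (sections 6.3 and 6.4): the nominal gap from Visit 3 is 28 days, the visit tolerance is -3 days, and the stool may be up to 3 days before the visit. The earliest stool is at 28 - 3 - 3 = 22 days.
- Visit 2, for a user who stops at Visit 1: anything from roughly the time needed to confirm eligibility and ship a kit, up to 30 days.

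The trial's own washout therefore guarantees about 22 days before the Visit 4 stool. Criterion 20 guarantees none before the Visit 2 stool.

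**2. Effect on the estimates**

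Inputs from the documents: 12 participants, 6 per sequence (sections 6.2 and 8.0). Assumptions: k prior users among the 12; the same residual effect f at Visit 2 in each; f gone by Visit 3; f in the same direction as the HAMS-AB effect d. A negative f reverses the signs.

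*Pre/post HAMS-AB change.* An affected HAMS-AB-first participant contributes d - f. A control-first participant uses the Visit 4 baseline and contributes d. Each user has probability 1/2 of receiving HAMS-AB first, so the expected bias in the mean of 12 is -(k/2)(f/12) = -kf/24. For k up to 6, the worst case is -kf/12, when all users receive HAMS-AB first.

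*HAMS-AB minus control contrast of changes.* A HAMS-AB-first user contributes (d - f) - 0 = d - f, and a control-first user contributes d - (-f) = d + f. Each moves the mean by f/12, down or up. With a the number of users in the HAMS-AB-first sequence, the shift is (k - 2a)f/12. Under 6:6 randomization its mean is 0 and its SD is (f/12)√[k(12 - k)/11].

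| k | Expected bias, pre/post | Worst case, pre/post | Contrast: mean | Contrast: SD | Contrast: largest shift |
|---|---|---|---|---|---|
| 1 | -0.04f | -0.08f | 0 | 0.08f | 0.08f |
| 2 | -0.08f | -0.17f | 0 | 0.11f | 0.17f |
| 4 | -0.17f | -0.33f | 0 | 0.14f | 0.33f |
| 6 | -0.25f | -0.50f | 0 | 0.15f | 0.50f |

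With k = 2, the chance that both users fall in the same sequence is 30/66 = 45%. With k = 4, the chance that the sequences differ by two or more users is 1 - 225/495 = 55%.

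*Scale.* With 12 paired differences, the 95% confidence interval half-width is 2.201/√12 = 0.64 SD of the differences. If f were as large as 1 SD of those differences (an assumption), one user would move the contrast by 0.08 SD.

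**3. Comparison that avoids the baseline**

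Comparing the end-of-period stools (Visit 3 against Visit 5) does not use Visit 2. It would be touched only if the old product's effect lasted through to Visit 3.

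**The case against.** The strongest case against the point is that its consequence is speculative and partly contained. The documents do not say how many users will enrol (possibly none), how long an effect lasts or which way it runs. A probiotic or a different fiber need not shift a diversity index as HAMS-AB does. Section 3.2 lists screening as the first study period, so agreement to stop is naturally read as starting at Visit 1. Confirming eligibility needs a C-peptide result and sometimes autoantibodies, so a same-day baseline is unlikely. Criterion 5 lets the investigator exclude any condition that could confound the results. Other medication use is recorded at Visit 2, and diet is recorded around each stool.

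All of this limits the size. None of it sets a minimum interval. The diet recall covers 24 hours and can miss a product stopped days earlier.

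A reader might infer three stronger claims that the documents do not support:

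- *Only a Visit 2 on days 28 to 30 would match the trial's washout.* The trial accepts a Visit 4 stool at about day 22, and section 3.1 cites 3- to 4-week washouts in other studies. A user may also have stopped before Visit 1.
- *This is the one relevant exposure without a look-back.* Criterion 19, on high-fiber and vegetarian diets, is judged by history and has no look-back period either.
- *The randomized comparison is biased in a known direction.* Its expected bias is zero; what remains is chance imbalance and added spread.

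**Conclusion.** The gap is real. As written, criterion 20 permits a period-1 baseline taken soon after a fiber supplement or probiotic was stopped, while the period-2 baseline is protected by a washout. The pre/post HAMS-AB change, the form in which section 8.0 describes the diversity index, has an expected bias of -kf/24 that randomization does not remove. The HAMS-AB minus control contrast of changes gains noise but no expected bias.

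The absolute size cannot be stated, because k, f and the direction of f are all unknown. Any percentage of the treatment effect would need a further assumption about f relative to d: if f = d, one user moves the contrast by 1/12, or 8%, of the effect; if f = d/2, by 4%. With no prior users there is no effect. Confidence is high that the interval is missing and low on how much it matters. This is a cheap improvement and not a threat to the trial.

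**What to change.** - Amend criterion 20 so that fiber supplements and probiotics have been stopped for at least the trial's own washout interval (4 weeks, with the same visit and stool tolerances) before the Visit 2 stool, and are not taken again until after Visit 5.
- For users who stop at Visit 1, book Visit 2 late in the existing window. With the same tolerances, that means day 25 to day 30: a stool 3 days before a day-25 visit falls on day 22, the earliest the trial accepts at Visit 4. Count time already off product for those who stopped earlier.
- Record the product and its stop date at Visits 1 and 2.
- State a sensitivity analysis of the microbiome and SCFA outcomes that leaves out recent users, and report how many there were.

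The cost is amendment wording, two data fields and one added analysis. Prior users wait about 3 to 4 weeks between Visits 1 and 2. The sample size stays at 12. This point requires no longer screening window and no change to the antibiotic criterion.

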53 EARLY TERMINATION OF A STUDY PARTICIPANT

[figure not shown]
Treatment will stop and the subject will return for an exit visit if any of the following conditions occur:

- withdrawal of consent
- pregnancy (female participants)
- any medically important event such as a concurrent illness or complications

- any investigator judgment

6.0 – STUDY PROCEDURES

6.1 STUDY DESIGN

6.2 RANDOM ASSIGNMENT

Subjects will be randomly assigned (6 in each arm) to either HAMS-AB plus a recommended diabetic diet or control diabetic diet alone [49, 50] for the first 4 week of treatment period. After a suitable washout period during which participants do not need to follow the recommended diet or use the supplement, subjects will continue for 4 weeks after a cross-over. All participants will be expected to follow the guidelines for a healthy diabetic diet during the study period, except for during the 4-week washout period.

A computer-based randomization plan will be prepared by the principal investigator. The document will be kept by the study team for use. As a subject is screened and qualifies, he/she will be assigned in order of screening date on the computer-generated document. One master list will be maintained in a confidential central shared folder for use. Subjects will be replaced on an ongoing list if they drop out.

Participants will be instructed to consume HAMS-AB with food, such as apple sauce or oatmeal, in two divided doses at breakfast and dinner at a total daily dose to be calculated as has been previously described for children: 10g plus 1g per year of age daily [44]. The prebiotic will be dispensed by the Investigational Drug Services (IDS) at Indiana University.

HAMS-AB will be in the form of acetylated and butyrylated **HYLON® VII** corn starch.

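### The randomisation list is written and kept by the principal investigator and held for use by the study team, so the coming sequence can be known before eligibility judgements, Visit 2 and replacements

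*Combined protocol and SAP*

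**What the plan says.** Section 6.2 states who makes the list: "A computer-based randomization plan will be prepared by the principal investigator". Two sections say who keeps it, and they differ. Section 4.5 has "Randomization lists will be kept by the PI", while section 6.2 has "The document will be kept by the study team for use" and then "One master list will be maintained in a confidential central shared folder for use".

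The allocation is fixed in total: "Subjects will be randomly assigned (6 in each arm) to either HAMS-AB plus a recommended diabetic diet or control diabetic diet alone". The rule for filling slots is "As a subject is screened and qualifies, he/she will be assigned in order of screening date on the computer-generated document". The schedule in section 6.3 and the Visit 2 text in section 6.4 place the act of randomisation at Visit 2, up to 30 days after screening: "Study Randomization to either supplement or standard of care diabetes management and a diabetic diet".

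Three other provisions bear on the point:
- Section 5.2, criterion 5, excludes a youth for "Any condition that, in the investigator's opinion, may compromise study participation or may confound the interpretation of the study results".
- Dropouts are replaced from an ongoing list (section 6.2). Youths who miss 20% of prebiotic doses (section 3.2), or who come to meet an exclusion criterion during the study (section 5.2), are also replaced. The sequence a replacement takes is not stated.
- The comparator is a recommended diet without placebo. Only the CGM sensor is called blinded (section 6.3).

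The plan describes no list holder outside the study team, no sealed envelopes, no one-at-a-time release and no access limits within the team.

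**The concern.** Randomisation protects against selection only if those who decide on entry cannot see what comes next. Here the plan states a procedure that makes the next sequence visible to at least one decision-maker. It does not merely leave concealment undescribed.

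Three decisions could then depend on the coming sequence: whether criterion 5 is invoked, how Visit 2 is timed, and whether and when a participant is replaced. There is room for such judgement, since up to 24 youths are screened for 12 places. Section 8.0 also sets intention-to-treat analysis aside, so replaced participants are not clearly retained in the analysis.

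At stake is the comparability of two sequences of six. Section 1.2 says the pilot's results are meant to support a fully powered study, so a selection effect could be carried into that study's assumptions.

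**Working it through.** **The plan's own figure.** The 12 rests on a cited rule of thumb, with no alpha, power, effect size or SD, so there is no power calculation to reproduce. The counts agree: 6 + 6 = 12, and 50% of 24 screened = 12. Nothing below changes the sample size.

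**How predictable is the next assignment?** Inputs: n = 12 and a 6:6 split (section 6.2), with past assignments visible because control is diet alone.

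- List readable: 12 of 12 known (100%).
- Single 6:6 list, concealed: the best guess is the sequence with more slots left. Expected correct guesses = n/2 + (2^n / C(n, n/2) − 1)/2 = 6 + (4096/924 − 1)/2 = 6 + (4.433 − 1)/2 = 7.72 of 12, or 64%. An exact recursion gives the same value.
- Simple randomisation: 6 of 12 (50%).
- Concealed random blocks of 2 and 4, by simulation: 8.6 of 12 (72%). The guess needs only the running totals, not the block sizes. Small blocks would therefore be more predictable than one concealed 6:6 list.

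**What does foreknowledge do to the treatment contrast?** Give each youth a stable level a, a change d from period 1 to period 2, and a treatment effect τ. Carry-over is set aside.

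- HAMS-AB first: HAMS-AB minus control = period 1 minus period 2 = τ − d.
- Control first: HAMS-AB minus control = period 2 minus period 1 = τ + d.
- Average of the two sequence means: τ + (mean d in control-first − mean d in HAMS-AB-first)/2.

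The level a drops out. Half of any between-sequence difference in trend remains. As a check under assumed values, a stable shift of 0.5 between-subject SD between sequences gave a bias of 0.50 SD in a first-period comparison and 0.00 in the within-person contrast.

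**Which readings lack this protection?** In the section 6.3 schedule HbA1c is drawn at Visits 2 and 5 only, apart from early termination. With no value at the end of period 1, HAMS-AB and control cannot be contrasted within a youth. Any randomised HbA1c comparison is six against six:
- comparing Visit 5 values takes the full between-sequence difference in level and trend;
- comparing change from Visit 2 takes the full difference in trend.

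Trend may well vary, because youths enter 4 to 36 months after diagnosis. The documents give no variance of trend for any outcome, so no bias in outcome units can be computed.

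**Do the timing statements fit together?** Section 6.2 orders slots by screening date once a youth qualifies; sections 6.3 and 6.4 randomise at Visit 2. The two can coexist if one sets the order and the other the act. The text does not say who takes the next slot when a later-screened youth reaches Visit 2 first.

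**The case against.** The strongest reply is the crossover. Every completer receives both conditions, so foreknowledge can affect only the order, and stable differences cancel. This stands for the within-person contrast, and it limits the seriousness of the point. It does not cover HbA1c or differing trends. Section 8.0 names plain t-tests with no period or sequence term.

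A second reply is that the folder is called confidential and its access rights are not given. This stands in part. A reader might infer that everyone who enrols already knows every sequence. The documents support that only for the principal investigator; for the study team, the sequence can be known.

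A third reply is that ordering by screening date leaves no choice among waiting youths. This also stands. A reader might picture the team choosing which of several qualified youths takes a given slot, and might attach an imbalance in SD units to that. The stated rule excludes this choice, so such a figure would describe a different procedure. Discretionary exclusion and replacement remain open.

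Two further inferences go too far. Durability is not a six-against-six comparison, because section 3.1 assesses it in those who received the prebiotic. Nor does anything show that baseline stool or diet data are altered: stool is collected at home, diet is ideally self-recorded, and no text tells families the sequence before Visit 2. Collecting both before release is simply a costless safeguard.

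**Conclusion.** The concern holds in a limited form. As written, allocation is not concealed from the principal investigator and need not be concealed from the study team. A reader of the list knows 12 of 12 assignments, against 7.7 of 12 (64%) guessable from a concealed single 6:6 list.

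The exposure lies mainly in between-sequence comparisons, HbA1c above all, and in any between-sequence difference in trend, of which the within-person contrast takes half. Its size cannot be derived from the documents, and nothing in them shows that selection has occurred.

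Two assumptions underlie this. The trial is treated as open because control is diet alone and no blinding of participants or staff is described; the documents do not use the term. The 64% assumes one list of 12 with past assignments visible and no replacements. This is a cheap improvement worth making, not a flaw that invalidates the design.

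**What to change.** In sections 4.5 and 6.2, have the biostatistician or Investigational Drug Services generate and hold the list, and remove it from the principal investigator, the study team and the shared folder. Both groups are already in the trial: Investigational Drug Services dispenses HAMS-AB, and Biostatistics is named in the confidentiality section. State one holder, so that the two sections agree.

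Release one assignment at a time at Visit 2, after eligibility is recorded and the baseline stool sample and diet recall are in hand. Replace screening-date order with order of randomisation, so that section 6.2 agrees with 6.3 and 6.4. State in advance which sequence a replacement takes, and leave that to the list holder.

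Keep the single 6:6 list, concealed. Blocks of 2 and 4 would raise guessability to 8.6 of 12 (72%).

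The cost is a short amendment and a call to the list holder at each Visit 2. No extra participants, visits or staff are needed.

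### The principal investigator writes the randomization list, and the PI or the study team keeps it with no concealment step, so the next sequence can be known while eligibility is being decided

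*Combined protocol and SAP*

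**What the plan says.** Section 6.2 (Random assignment) makes the PI the author of the list: "A computer-based randomization plan will be prepared by the principal investigator". On custody it says "The document will be kept by the study team for use", and adds "One master list will be maintained in a confidential central shared folder for use". Section 4.5 (Study related information) says otherwise: "Randomization lists will be kept by the PI".

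On use, section 6.2 says that once a subject has been screened and qualifies, "he/she will be assigned in order of screening date on the computer-generated document". Six subjects are to go to each order. On losses it says "Subjects will be replaced on an ongoing list if they drop out".

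Section 6.4 places the act at Visit 2: "Study Randomization to either supplement or standard of care diabetes management and a diabetic diet". The schedule in 6.3 allows up to 30 days between screening and that visit. One exclusion in section 5.2 is a matter of investigator opinion, covering any condition that "may compromise study participation or may confound the interpretation of the study results".

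The comparator is dietary guidance alone, without placebo. The documents do not use the term open-label, but that is the effect.

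**The concern.** Randomization protects a comparison only if the person deciding whether and when a subject enters cannot foresee the assignment. Here the list's author is the PI, both stated holders belong to the trial team, and the one safeguard named is that the folder is confidential. Earlier assignments are visible because one condition involves a supplement and the other does not.

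There is room to act on such knowledge. Up to 24 are screened for 12 places, one exclusion is discretionary, and the date of Visit 2 can move within a 30-day window. If sequence influences who enters or when, the two sequence groups may differ for reasons other than chance. Any comparison between sequences then inherits that difference. The pilot's stated purpose is to estimate effect sizes for later trials, so a distortion would carry forward.

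**Working it through.** **1. Custody, side by side.** Section 4.5: the PI keeps the lists. Section 6.2: the study team keeps the document, with a master copy in a shared folder. The two sections must be reconciled, but neither names a holder outside enrolment. Sealed envelopes, central release, a log of eligibility before release and a limit on who may open the folder are all absent. Investigational Drug Services (IDS) appears in 6.2 only as dispenser.

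**2. Order of use.** Eligibility is settled between screening and Visit 2; randomization is at Visit 2. Places are taken in screening-date order among those who qualify. If a subject screened later qualifies first, the text does not settle who takes which place.

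**3. How predictable is the next assignment?** The plan's own count is consistent: 6 + 6 = 12. Expected correct predictions out of 12:

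- List seen: 12.
- Concealed simple randomization: 12 × 1/2 = 6.0.
- List hidden, past assignments visible, balance forced: for a block of size 2n, the best guess is right n + 2^(2n−1)/C(2n,n) − 1/2 times.
  - One block of 12 (n = 6): 6 + 2048/924 − 0.5 = 7.7.
  - Three known blocks of 4 (n = 2): 3 × (2 + 8/6 − 0.5) = 8.5.
  - Six known blocks of 2 (n = 1): 6 × (1 + 2/2 − 0.5) = 9.0.

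The block size is not stated, so 7.7 to 9.0 is a range under assumption. It is also the residual predictability that would remain with the list hidden.

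**4. Which comparisons are exposed?** Let t be the treatment effect and p the period effect (period 2 minus period 1). A person's HAMS-AB minus diet difference has expectation t − p if HAMS-AB came first and t + p if diet came first. The person's own level cancels.

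- *Paired and period-adjusted.* The average of the two sequence means is t, whatever the group sizes. Selection on a person's level has no effect; only selection on expected trend or response could matter. Stool is collected at Visits 2 to 5 and the MMTT is done at Visits 3 and 5, so the data permit this contrast.
- *Paired but not period-adjusted.* The expected mean is t + p × (n diet-first − n HAMS-AB-first)/12. At 6:6 the period term vanishes. At 7:5 it is 2/12 = 0.17 of p in absolute value; at 8:4 it is 4/12 = 0.33 of p. The first section 8.0 names chi-square and t-tests for simple comparisons and a pre/post diversity index; it commits to neither pairing nor period.
- *HbA1c.* The schedule gives HbA1c at Visits 2 and 5 or early termination, with none at the end of period 1 or the start of period 2. For a completer the change spans both conditions and the washout. Treatment can then be compared only through sequence, 6 versus 6, which is where selection would matter most.

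**5. Replacement.** Replacing on an ongoing list may mean filling the vacated place or taking the next one. The first keeps 6:6; the second need not. Section 3.3 stops recruitment at 12 completers without restating the split.

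**The case against.** The documents do not say that anyone consults the list before judging eligibility. Assignment follows qualification, the folder is called confidential, and screening-date order is an objective rule that limits choice. Every participant is meant to receive both conditions, so foreknowledge alters order rather than treatment received. All of this stands. It makes the problem smaller than in a parallel-group trial, but it does not supply concealment.

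Several stronger readings are tempting and are not supported:

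- A reader might infer that every next sequence is known to all who decide eligibility. For the PI, as author, knowledge follows. For other staff the text shows only that the list is available.
- A reader might see a contradiction between assignment on qualifying and randomization at Visit 2. The two are compatible.
- A reader might suppose that durability and carryover will be tested 6 versus 6. Section 3.1 assesses durability among those given the supplement, and no carryover test is specified.
- A reader might size the bias by substitution: replacing one average participant in six by one 1 SD higher moves that mean by 1/6 = 0.17 SD, and an exchange between sequences moves the difference by 0.33 SD. The arithmetic is right, but the substitution is invented. It concerns level, whereas the primary outcome is change, and it lies well inside the chance standard error of a 6-versus-6 difference, √(1/6 + 1/6) = 0.58 SD.
- Withdrawal and re-entry decisions might be added to the list. Once treatment starts the sequence is visible anyway, so hiding the list would not blind them.

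**Conclusion.** The concern holds as a weakness of allocation concealment that should be corrected. The plan places the list with its author or with the trial team and describes no step that withholds the next assignment until eligibility is fixed. That permits selection by sequence; it does not show that selection occurs, and the documents give no basis for a bias figure.

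For outcomes measured in both periods, a complete paired analysis adjusted for period would be little affected, but the plan does not commit to that analysis. For HbA1c the exposure is direct, because only a between-sequence comparison of treatment is possible. It would be too strong to say that replacement breaks the 6:6 split; the text leaves this unclear. The conclusion assumes that the study team screens and enrols, and that no unwritten procedure restricts access to the folder. No sample-size figure changes.

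**What to change.** Reconcile sections 4.5 and 6.2 so that one party outside enrolment generates and holds the list, with no access for the PI or screening staff. IDS is a natural candidate because it already dispenses HAMS-AB, but its agreement is needed; the documents do not say that it offers this service. That party releases one assignment at Visit 2, only after eligibility has been confirmed and logged. Replace screening-date order with order of confirmed eligibility at Visit 2.

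For replacements, use the next concealed assignment from a pre-generated extension of the same list. They should not openly inherit the drop-out's sequence, because the team already knows that sequence and the replacement's allocation would be certain in advance. Since this can depart from 6:6, state in the first section 8.0 that the treatment contrast is within-person and includes period.

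Some predictability from visible past assignments and forced balance will remain; keeping any block size from enrolling staff limits it. The cost is modest administrative work for the list holder, amendments to sections 4.5 and 6.2, and a sentence on the analysis. No visits or procedures are added, and the target of 12 is unchanged.
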